### 2.3.2 KNOWN POTENTIAL BENEFITS

Patients enrolled in this study who are receiving the strategy-of-care or usual care may receive a benefit such as decreased mortality, or less frequent hospitalizations related to HF, or feel better faster, or have less myocardial injury,

AHF patients, if this study demonstrates sufficient safety to then test in a future efficacy study, which if positive will show that and ED AHF strategy-of-care has beneficial clinical outcomes. If the study shows that a LUS guided ED AHF strategy-of-care is not safe with the current study design, future patients may be spared the cost of ineffective ED AHF management, and spared the potential for any possible side effects.

### 3 OBJECTIVES AND PURPOSE

#### *Objectives:*

**1:** To determine whether a strategy of care – early LUS guided, protocol-driven ED AHF therapy – leads to more rapid resolution of congestion.

**2:** To demonstrate feasibility of recruitment and compliance with study protocol to inform future study design and enrollment projections

#### *Purpose:*

This pilot trial is designed to provide the necessary and sufficient information for a larger, definitive trial.

*Our overarching hypothesis:* A protocol-driven ED AHF strategy-of-care, guided by lung ultrasound (LUS), will lead to improved 30 and 90-day outcomes. Importantly, this strategy-of-care will utilize only currently available therapies – non-invasive ventilation, vasodilators (sublingual, topical, and/or IV), and IV loop diuretics. Successful completion of our specific aims will provide the necessary and sufficient information to determine whether a LUS guided ED strategy leads to more rapid and sustained decongestion. A subsequent multi-center, randomized, simple, strategy-of-care trial, will test whether LUS guided, protocol-driven ED AHF management reduces 30 and 90-day post-discharge days alive and out of hospital (DAOOH).

We focus on a subset of AHF patients. If successful, we may expand the patient population in future studies. However, the following critical issue needs to be addressed prior to initiation of a large, simple, efficacy study: does ED AHF management, guided by LUS, lead to rapid and sustained decongestion above and beyond usual care? Although this pilot study focuses solely on ED management, we will assess patients throughout hospitalization, carefully following management to inform subsequent trial design. To minimize heterogeneity of treatment, we exclude patients in cardiogenic shock or hypertensive emergency. This project will generate new, critically important knowledge about the ED phase of AHF management.

### 4 STUDY DESIGN AND ENDPOINTS

#### 4.1 DESCRIPTION OF THE STUDY DESIGN

A multi-center, prospective, randomized, controlled, unblinded strategy-of-care pilot trial. All potential ED patients will receive an initial LUS scan. Performing LUS is within the standard of care and will be done at no cost to patients. It is not frequently used however, either for diagnosis, prognosis, or to guide clinical therapy. However, treating clinicians will be blinded to these results to minimize contamination of the usual care arm. If clinicians choose to perform their own LUS, those patients will not be excluded. Patients who provide written informed consent and meet all inclusion and no exclusion criteria will be randomized 1:1 to our LUS-guided strategy-of-care vs. usual care. While no further LUS guided intervention will occur for usual care patients, similar to our LUS-guided arm, serial LUS assessments will occur throughout hospitalization as well as pre-specified biomarkers and physical exam. For patients randomized to the strategy-of-care arm, the LUS guided protocol will be initiated and continued until there is a decrease in B-lines to  $\leq 15$  or 6 hours of care has been delivered or patient has left the ED, whichever comes first. Trained research personnel will acquire LUS images. All images will be stored and overread by an independent, expert ultrasonographer blinded to treatment arm.

Safety of patients are paramount. If a potential life threatening etiology is identified, the clinical team will be made aware immediately, irrespective of randomization arm. These occurrences will be recorded in the eCRF. While this will be a rare event, we will a priori establish that an additional patient will be accrued into the study and an additional modified intent to treat population for analysis will be performed, excluding these patients where a life-threatening etiology was identified (i.e. pericardial tamponade).

For patients who do NOT meet eligibility criteria, the results of their LUS will be provided to the clinical team as requested, as these patients are no longer at risk for contamination of the usual care arm.

#### 4.2.1 PRIMARY ENDPOINT

B-lines  $\leq 15$  at the conclusion of ED AHF management (i.e. patient has left the ED) or maximum of 6 hours after enrollment, whichever comes first.

#### 4.2.2 EXPLORATORY ENDPOINTS

The following table lists the exploratory endpoints

Table 3: Exploratory Endpoints	
Total DAOOH through 30 and 90 days post-discharge	Association of B-lines at discharge and 30 and 90 day outcomes
Change in biomarkers from presentation to pre-discharge	Association of baseline, discharge, and change with 30 and 90 day outcomes
Time to reach B-lines <15	B lines < 15 at 24 hours and at discharge
Composite of 30-day all-cause mortality, cardiovascular (CV) re-hospitalizations, and CV emergency department (ED) revisits. CV endpoints are defined according to the 2014 ACC/AHA Key Data Elements and Definitions for Cardiovascular Endpoint Events.  Also for same endpoint, but through 90 days	All Cause readmissions, All cause ED re-visits
Change in physical exam findings and body weight from presentation to pre-discharge	Description of ED pharmacologic treatment
Description of hospital based AHF treatment	Inter and intraobserver agreement

## 5 STUDY ENROLLMENT AND WITHDRAWAL

### 5.1 PARTICIPANT INCLUSION CRITERIA

- 1) Age  $\geq 21$  years
- 2) Presents with shortness of breath at rest or with minimal exertion
- 3) Clinical diagnosis of AHF and presence of > 15 total bilateral B-lines distributed in at least 4 zones on initial LUS
- 4) Hx of chronic HF and any one of the following:
  - i. Chest radiograph consistent with AHF
  - ii. Jugular venous distension
  - iii. Pulmonary rales on auscultation
  - iv. Lower extremity edema

## 5.2 PARTICIPANT EXCLUSION CRITERIA

- 1) Chronic renal dysfunction, including ESRD or eGFR < 45ml/min/1.73m^2.
- 2) Shock of any kind. Any requirement for vasopressors or inotropes.
- 3) SBP < 100 or > 175mmHg
- 4) Need for immediate intubation
- 5) Acute Coronary Syndrome OR new ST-segment elevation/depression on EKG. (troponin release outside of ACS is allowed)
- 6) Fever >101.5°F
- 7) End stage HF: transplant list, ventricular assist device
- 8) Anemia requiring transfusion
- 9) Known interstitial lung disease
- 10) Suspected acute lung injury or acute respiratory distress syndrome (ARDS)
- 11) Pregnant or recently pregnant within the last 6 months

## 5.3 STRATEGIES FOR RECRUITMENT AND RETENTION

Each site will have a lead PI and US Director, along with a dedicated study team. This study team, comprised of research assistants and coordinators, will perform both electronic screening (via tracking boards) and maintain a continuous physical presence in the ED to identify patients. All sites currently screen patients at minimum 16 hours each day, 5 days per week. Additionally, Detroit has a 24/7 program, Vanderbilt does this 6 days a week, and Indianapolis has 6 hours of coverage on the weekends. These methods have been utilized with success in previous trials. Standard computerized internet-based screening logs will be maintained to identify ED AHF patients admitted to the hospital and record screen failures. All patients with a final diagnosis of AHF at the time of hospital discharge will be considered to have AHF.

As we aim to design a pragmatic, ED-based study our inclusion/exclusion criteria are relatively broad compared to other therapeutic clinical trials.

### *Screen Failures:*

Patients who sign an informed consent but who are not randomized will be considered Screen Failures. Only data for randomized patients will be entered into the CRF. Serious adverse events should be reported for these patients from the time the ICF is signed through the time that the patient is declared a screen failure. One expected reason for screen failure will be the absence of > 15 B-lines at baseline.

## 5.4 PARTICIPANT WITHDRAWAL OR TERMINATION

### 5.4.1 REASONS FOR WITHDRAWAL OR TERMINATION

In accordance with the guiding principles of the Declaration of Helsinki, any patient is free to withdraw from participating in this study at any time and for whatever reason, specified or unspecified, and without prejudice. Investigators should attempt to determine the cause of withdrawal and, if desired by the patient, to make it possible for the patient to continue to participate in the study. The extent of a patient's withdrawal from the study (i.e. withdrawal from further study treatment, withdrawal from any further contact, etc.) should be documented. Every effort should be taken to follow all randomized patients, to the extent that the patient will allow, for the full follow-up period.

Investigators may discontinue study treatment for any other reasons concerning the health or well-being of the patient.

The reason for and date of study discontinuation and the reason for and date of withdrawal from the study must be recorded on the CRF. If study is discontinued because of an adverse event or a clinically significant abnormal laboratory test result, evaluations will continue until the event has resolved or stabilized or until a determination of a cause unrelated to the study procedure is made. The specific event or laboratory finding(s) must be documented. All evaluations should be performed, according to the protocol.

#### 5.4.2 HANDLING OF PARTICIPANT WITHDRAWALS OR TERMINATION

The Full Analysis Set (FAS) will include all randomized patients. In accordance with the intent-to-treat principle, patients will be analyzed by the group to which they were randomized. Misrandomized patients (patients randomized in error who did not receive any study intervention) will be excluded. Analyses in the FAS will constitute the main efficacy results for the primary and secondary study efficacy endpoints.

The Per Protocol Set (PPS) will be a subset of the FAS and will exclude patients with major protocol violations. The major protocol violations that will result in exclusion from the PPS will be identified prior to unblinding the treatment assignments for final analysis. Patients will be analyzed in the treatment group to which they were randomized. Results of analyses in this analysis population will support the primary efficacy analyses in the FAS.

#### 5.5 PREMATURE TERMINATION OR SUSPENSION OF STUDY

The study is overseen by a DSMB. They may terminate the study at any time if the safety of patients is at jeopardy.

## 6 STUDY AGENT

[figure not shown]
### 6.1 STUDY AGENT(S) AND CONTROL DESCRIPTION

This study will test a strategy-of-care vs. usual care for ED AHF management. Only therapies already in use will be applied. For example, NIV, IV loop diuretics, and nitrovasodilators. The usual care arm will also follow the treatment protocol, unless the clinician explicitly states no further treatment is warranted based on their clinical assessment to better reflect real-world conditions. No drugs or therapies that are not approved by the FDA will be allowed.

#### 6.1.1 DOSING & DOSE ESCALATION

The algorithm below outlines the treatment protocol.

- All enrolled patients should receive IV furosemide per the protocol box.
  - IF patients already received furosemide prior to the time of enrollment, BRANCH point.
    - Patients in usual care arm will NOT receive any further diuretic.
    - Patients in LUS arm will receive further diuretic to equal 2x single oral dose. For example, if the patient usually takes 80 BID at home, but then already received 40mg at arrival to the ED, if in the LUS arm, would receive an extra 120mg. (200 is the maximum single time dose.)
- Clinical assessments should be recorded irrespective of treatment arm. However, the initial ED LUS assessment will be considered Time 0.

\*IMPORTANT – the clinical assessment alone arm will ALSO have LUS performed – however, these results will NOT be shared with clinical caregiving team

\*\* ALL enrolled patients will be re-assessed at least twice during their ED stay. First re-assessment will occur within 2-4 hours of first TREATMENT. Assessments outside this window are NOT allowed for study purposes unless at the discretion of the investigator. The second re-assessment will occur EITHER 2-4 hours after the first OR prior to discharge. IF the pre-discharge assessment is missed in the ER, this should occur ASAP after arrival to the hospital floor.

NOTE: the maximum dose allowed at any one time of IV Lasix is 200mgIV.

NOTE: For additional IV loop diuretic doses, the options under Restart Algorithm are three options. Clinical/Research team may choose one of the three loop diuretic dose options.

NOTE: for both arms: After each reassessment, the clinical physician will be asked:

1. “In your clinical opinion, is the patient still volume overloaded?” (Yes, No, Not sure)
2. If Yes, then the following question will be asked: “Do you think the patient warrants additional treatment now?”
3. If Yes, then FOR THE CLINICAL ASSESSMENT ARM ONLY: treatment will occur **per the algorithm**. (Patients in the LUS intervention arm will ONLY receive further therapy guided by LUS)

NOTE: The protocol is not optional. Of course, patient safety comes first, similar to all other interventional trials. However, similar to other interventional studies, once randomized, the study protocol should continue forward. If, in the opinion of the investigator, continuing treatment is potentially unsafe (i.e. SBP has decreased significantly, very brisk diuresis) uptitration per protocol may be held.

The protocol continues until 6 hours after randomization. Even if the patient is on the floor and under the care of the inpatient team. If, in the opinion of the investigator, the protocol should not be continued once on the hospital floor, this is allowed and should be marked on the case report form.

---

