## Image acquisition

- Patient supine
- 45 degrees of bed elevation (as possible, if not possible please note on CRF)

[figure not shown]
- Starting off on the **Right** in **Zone 1**: you want the indicator towards the patient's head. Identify ribs by shadowing and identify a rib space (see image below)
- Label R1
- Then turn 90 degrees with **indicator towards patient's right** so you are still in a rib space but the probe is **HORIZONTAL**
- Scan within the zone until you see the area of most B lines
- Record 6 second clip (this should include both inspiration and expiration)
- Repeat the above for Right zones 2-4 and Left zones 1-4
- Obtain **VERTICAL** R4 and L4 zones
- 10 TOTAL videos
- After you leave the bedside, record the number of B lines on a standardized data collection form or in REDCap

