#### Lung Ultrasound (LUS) Protocol

To best determine the potential value of EVLW measurements using LUS, we will assess patients at multiple timepoints throughout hospitalization. (See Figure 1 – Trial design flow below)

Figure 1: Trial Schematic

For diagnostic purposes, previously published protocols have been the most well-studied.

Each LUS scan consists of 8 sectors as seen in figure 2. (Figure reproduced from Volpicelli et.al.7) Trained research personnel will record and count B-lines in each sector as visualized through one respiratory cycle at each of the time points listed in the Figure. At minimum, each stored video clip will be 6 seconds in length. The total number of B-lines for all 8 sectors will comprise the overall score. With training, the entire scan takes less than 10 minutes.

As patient positioning may impact B-lines, patients will be placed at approximately 45 degrees for all scanning. The CRF will be marked if patients are unable to lie at this angle.

- An 8 zone LUS scan will be done at the following times:
  - T00: initial LUS scan (in ED for screening and eligibility)
  - T02: 2-4 hours after initial treatment (in ED) (+/- 30 minutes)
  - T06: 2-4 hours after T02 or pre-ED discharge, whichever comes first (+/- 60 minutes)
  - HD2: 24 hours after initial scan (Day 2) (+/- 6 hours)
  - HD3: 48 hours after initial scan (Day 3) (+/- 8 hours)
  - HD4: Day 4 (anytime during day)
  - HD5: Day 5 (anytime during day)
  - HD6: Day 6 (anytime during day)
  - HD7: Day 7 (anytime during day)
- **If standard care arm do NOT notify the provider of the results**

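### The dose-choice note in 6.1.1 does not stop staff who know a usual-care patient's B-line count from helping to choose that patient's repeat diuretic option

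*Combined protocol and SAP*

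**What the plan says.** All references are to the combined protocol and SAP.

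- **Who chooses the repeat option (6.1.1).** For additional IV loop diuretic there are three options under the restart algorithm, and "Clinical/Research team may choose one of the three loop diuretic dose options". The note names no arm.
- **Usual care uses the algorithm (6.1, 6.1.1).** "The usual care arm will also follow the treatment protocol", unless the clinician states that no more treatment is warranted. Under 6.1.1, if the clinical physician answers Yes to both reassessment questions, a patient in the clinical-assessment arm is treated according to the algorithm.
- **Who holds the count (4.1, 17.1, 17.3).** "Trained research personnel will acquire LUS images" (4.1) and "Trained research personnel will record and count B-lines in each sector" (17.3). The scanner is told: "After you leave the bedside, record the number of B lines on a standardized data collection form or in REDCap" (17.1, Image acquisition). Patients in both arms are scanned serially.
- **From whom it is withheld in usual care.** In 4.1, "treating clinicians will be blinded to these results to minimize contamination of the usual care arm". In 6.1.1, "these results will NOT be shared with clinical caregiving team". In 17.3, "If standard care arm do NOT notify the provider of the results".

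**The concern.** The trial compares treatment guided by LUS with treatment that is not. In usual care this depends on keeping the B-line count away from treatment decisions, and 4.1 gives that as the reason for withholding it. The withholding rule is written around the clinical team. The dose-choice note opens one treatment step to the research team as well, and that team produces the count. Nothing in the text separates the two roles.

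If a person who knows the count helps to choose a usual-care patient's option, treatment in the comparator is partly informed by LUS. The primary comparison, the proportion reaching the B-line threshold, could then move for a reason the analysis cannot detect, because no listed data item records who chose or what they knew. This is a pilot meant to inform a definitive trial, so an unmeasured leak in the comparator also weakens what can be carried forward.

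**Working it through.** **Step 1. Set the rules side by side.**

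| Question | Text | Reaches research staff in usual care? |
|---|---|---|
| Who may choose the repeat option? | 6.1.1: clinical or research team, no arm limit | Yes |
| Who acquires and counts B-lines? | 4.1, 17.3: research personnel, both arms | Yes |
| From whom are usual-care results withheld? | 4.1: treating clinicians; 6.1.1: caregiving team; 17.3: provider | No |
| Who decides whether more treatment is given? | 6.1.1: clinical physician, two Yes answers | No |

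The first three rows together leave the gap. The fourth confines it to the choice among options after the physician has decided. The blinded core lab in 17.3 does not close it: that blinding protects the reading of images, and the core lab has no part in treatment.

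The neighbouring note in 6.1.1 is labelled as applying to both arms and restricts its third step to one arm. The authors marked arm limits where they intended them, and the dose-choice note carries none.

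**Step 2. Reproduce the plan's power (10.5).** Inputs: n = 59 per arm, control 25%, LUS arm 50%, two-sided alpha 0.05. With the pooled-variance normal approximation and no continuity correction:

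power = Φ{ [Δ√n − 1.96·√(2p̄(1−p̄))] / √(p₁(1−p₁) + p₂(1−p₂)) }, where p̄ is the mean of the two rates and √59 = 7.681.

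- Control 25%: Δ√n = 0.25 × 7.681 = 1.920; p̄ = 0.375, so 1.96 × 0.685 = 1.342; denominator √0.4375 = 0.661. Then (1.920 − 1.342)/0.661 = 0.874 and power = 0.809. The stated 81% is reproduced.

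**Step 3. Illustrate in both directions.** The shifted control rates are assumptions. No figure in the documents links the choice of option to the control rate. The LUS arm stays at 50%.

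- Control 30%: 0.20 × 7.681 = 1.536; p̄ = 0.40, so 1.96 × 0.693 = 1.358; denominator √0.46 = 0.678. Then 0.178/0.678 = 0.263 and power is about 60%.
- Control 20%: 0.30 × 7.681 = 2.304; p̄ = 0.35, so 1.96 × 0.675 = 1.322; denominator √0.41 = 0.640. Then 0.982/0.640 = 1.534 and power is about 94%.

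The 94% is no benefit. A control rate pushed down by how the option was chosen would enlarge the difference through bias.

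**Step 4. Direction.** Knowing that a count is high could push the chosen option one way. Knowing that it is low, or knowing the allocation in this unblinded trial (10.6.1), could push it the other way. The documents do not settle which would dominate.

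**The case against.** **Roles.** The note can be read as meaning the clinical team in usual care and the research team in the LUS arm. Nearby text leans that way, since usual-care treatment follows the clinician's assessment and it is the clinical physician who is asked. This is a fair reading, but the text does not state it, and no section keeps the person who scanned out of the choice. The point is therefore an unseparated role. A reader might infer that the protocol has the scanner set usual-care dosing, or that usual care is in effect LUS-guided. The documents do not say either.

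**The physician's decision comes first.** Repeat treatment in usual care requires two Yes answers from a physician who is not given the result. This stands, and it limits the point to the choice among options.

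**Size of the exposed group.** A branch in 6.1.1 bars further diuretic for usual-care patients who had furosemide before enrollment. If it also covers repeat doses, those patients never reach the choice. The text does not reconcile this branch with the rule that treatment follows the algorithm. In addition, the algorithm figure is not in the text available here, so neither the spread between options nor any arm limit inside the figure could be checked.

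**Power.** A reader might infer a loss of power from the 30% case alone. The documents do not support that, because the rate is assumed and the opposite shift is equally open.

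**Timing of the physician's questions.** A reader might also infer that asking these questions after the result is disclosed in the LUS arm spoils the planned comparison of B-lines with other markers of congestion. Sections 10.2 and 10.4.4 do not list those answers as a marker, and in the LUS arm they do not drive treatment. That inference fails.

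**Accepted contamination.** Section 4.1 keeps patients whose clinicians perform their own LUS, a more direct route for LUS to reach usual care. The gap described here adds to that. It differs in arising from the protocol's own wording, so the sponsor can close it.

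**Conclusion.** The point holds as a gap between two rules in the plan. The dose-choice note admits a group that holds the B-line count to a treatment step in usual care, and the withholding rule does not reach that group. The text permits count-informed participation in the choice; it neither directs it nor shows that it will happen.

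The exposure is the choice among three options, after a physician without the result has decided to treat, in a group that the prior-furosemide branch may make smaller. Effect size and direction cannot be determined from the documents. The figures of about 60% and 94% show only how sensitive the 81% is to a 5-point shift in the control rate either way, with the LUS arm held at 50% and 59 analysed per arm. The conclusion also assumes that the figure not available here contains no arm or role limit. It should be corrected because it undercuts a safeguard the plan itself sets out and is cheap to close.

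**What to change.** 1. In 6.1.1, reconcile the dose-choice note with the withholding rule. State that in the usual-care arm the rule extends to anyone who takes part in choosing the repeat option, so that staff who know that patient's B-line count take no part. Use the same wording in 4.1 and 17.3.
2. Add to the existing CRF, at each repeat dose, who chose the option and whether that person knew the LUS result. Any remaining contamination can then be counted and reported by arm.
3. Reconcile the branch on furosemide given before enrollment with the rule that usual-care treatment follows the algorithm, so that it is clear which usual-care patients can reach the choice at all.

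None of this judges or changes the dose options or the clinical rules. The cost is a few sentences of text, one extra CRF item and slightly more clinician time at reassessment.
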